4.7.2.2 Primary analysis: Missing Baseline Glucose Value

In a blind review of anonymised plasma glucose values, it was observed that the baseline glucose value, which is used for evaluation of the primary endpoint, is missing for one subject. Since plasma glucose levels were monitored at site by using an US FDA-approved glucose analyzer (Yellow Springs Instrument, YSI), a substitute baseline value can be obtained for this subject.

Even though some differences in the plasma glucose level are expected between local YSI measures obtained at site and clinical laboratory measures, it has been decided to use the baseline plasma glucose value from the YSI in the analysis for this subject. The actual pre-dose YSI value used for this subject will be reported in the Clinical Trial Report.

In a sensitivity analysis, the time to plasma glucose recovery will be analyzed without the subject missing the baseline clinical laboratory plasma value.

4.7.3 Secondary endpoints

- Plasma glucose recovery within 30 minutes, within 20 minutes, within 15 minutes, and within 10 minutes after study drug injection without administration of rescue IV glucose.
- Plasma glucose changes from baseline within 30 minutes, within 20 minutes, within 15 minutes, and within 10 minutes after study drug injection or at the time of rescue.

4.7.3.1 Confirmatory analysis

The key secondary incidence variables (plasma glucose recovery within 30 minutes, within 20 minutes, within 15 minutes, within 10 minutes, in hierarchical order for inference) will be analyzed using descriptive statistics (frequency and percentage) by treatment group. Inferential treatment group comparisons will be assessed via pairwise tests of independent binomial proportions (dasiglucagon versus placebo, GlucaGen versus placebo) using Fisher's exact test for each pairwise comparison.

CONFIDENTIAL

Sponsor:	Zealand Pharma A/S	Protocol Number:	ZP4207-16137
----------	--------------------	------------------	--------------

The key secondary endpoints of plasma glucose changes from baseline within 30 minutes, within 20 minutes, within 15 minutes, and within 10 minutes after study drug injection or at the time of rescue, will be analyzed with the plasma glucose changes from baseline at rescue carried forward in those subjects who require rescue IV glucose before plasma glucose ≥ 20 mg/dL recovery. Each of these changes from baseline variables will be analyzed using an Analysis of Covariance model, with treatment group modelled as a fixed effect and with the baseline plasma glucose modelled as a covariate. The dasiglucagon versus placebo treatment group difference will be evaluated inferentially as a least squares means contrast, using a two sided t-test at the 0.05 significance level, first for the 30 minute changes from baseline, and then sequentially for the 20 minute, 15 minute, and 10 minute variables, until the first failure to reject.

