3.1 Discussion of Study Design

This trial is a global, multicenter, randomized, parallel, double-blind, clinical trial confirming the efficacy and safety of dasiglucagon for insulin-induced hypoglycemia in subjects with T1DM. The subjects will be randomized 2:1:1 to receive a single fixed SC 0.6 mg dose of dasiglucagon, placebo, or a 1 mg dose of GlucaGen and followed for at least 28 days after receiving treatment. A total of 156 subjects with T1DM are expected to complete the treatment visit. This trial is planned to be conducted at 4 to 6 trial sites in the United States of America [US], Canada, and Europe.

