3.9 Sample Size

Due to requirements in the size of the safety database, the sample size is set to 78 subjects treated with dasiglucagon 0.6 mg. From phase 2, the median time to an increase of 20 mg/dL of the 0.6 mg dose was approximately 10 minutes. With a 2:1:1 randomization ratio for the three treatments, dasiglucagon 0.6 mg, placebo, and GlucaGen 1 mg, and assuming an exponential time-to-recovery distributions with median times of 10 and at least 20 minutes for dasiglucagon and placebo, respectively, a two-sided log-rank test will be able to detect a difference between dasiglucagon and placebo with 90% power with a follow-up time of 45 minutes at a 5% significance level with 78 subjects treated with dasiglucagon and 39 subjects with placebo. The median time-to-recovery for placebo is expected to be longer than 20 minutes, which means that the power will be greater than 90%.

4 Statistical Methodology

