4.15 Algorithms/SAS Codes

- **Tables that need descriptive statistics – continuous variables:**

```
PROC UNIVARIATE DATA=dset NOPRINT;
  VAR var1 var2 var3 ... varn;
  BY byvar; (optional)
  OUTPUT OUT=outname
  N=n MEAN=mean MIN=min MAX=max MEDIAN=median STD=std;
  RUN;
```

- **Tables that need frequency counts:**

```
PROC FREQ DATA=dset NOPRINT;
  BY byvar; (optional)
  TABLES var1*var2;
  OUTPUT OUT=outname;
  RUN;
```

- **Tables that need exact or asymptotic 95% CIs between groups for proportions:**

```
PROC FREQ DATA=dset;
```

CONFIDENTIAL

Sponsor:	Zealand Pharma A/S	Protocol Number:	ZP4207-16137
----------	--------------------	------------------	--------------

BY byvar; (optional)
*TABLES var1 * var2 / MEASURES RISKDIFF ALPHA=0.05;*
EXACT MEASURES;

RUN;

Notes: 1 Estimates are computed for 2x2 tables only

2 This code also gives exact 95% CIs within group for binomial proportions

- **Tables that need 95% CIs within group for binomial proportions:**

PROC FREQ DATA=dset;
BY byvar; (optional)
TABLES var1;
EXACT BINOMIAL;
RUN;

- **Tables that need 95% CIs within group for continuous variables:**

DATA outdata;
SET outname;
LCL=mean-(TINV(0.975,n-1)(std/SQRT(n)));*
UCL=mean+(TINV(0.975,n-1)(std/SQRT(n)));*
RUN;

- **Tables that require generalised linear modelling, including 95% CIs:**

PROC GENMOD DATA= dset;
CLASS class variables;
MODEL 'Responses / Attempts' = <effect> <treatment> /DIST=BIN;
LSMEANS treatment / DIFF CL;
ESTIMATE Drug 1 vs. Placebo' treatment 1 0 0 -1 /EXP;
ESTIMATE Drug 2 vs. Placebo' treatment 0 1 0 -1 /EXP;
ESTIMATE 'Drug 3 vs. Placebo' treatment 0 0 1 -1 /EXP;
BY byvar; (optional)
WHERE wherever; (optional)
RUN;

Note: (Treatment order: 1=drug 1,2= drug 2,3= drug 3, etc... 5= placebo)

- **Tables that require analysis of (co)variance and 95/90% CIs between arms for continuous variables:**

PROC GLM DATA= dset OUTSTAT=outset;
CLASS class variables;
MODEL response = <effect> <treatment> / SOLUTION;
*LSMEANS treatment / STDEERR PDIFF CL; *ADD: ALPHA=0.1 for 90% CIs;*
*ESTIMATE 'T1 - T2' treatment 1 -1 0; *or 'T2 - T1' treatment -1 1 0 if applic.;*
ESTIMATE 'T1 - T3' treatment 1 0 -1;
ESTIMATE 'T2 - T3' treatment 0 1 -1;
BY byvar; (optional)

CONFIDENTIAL

Sponsor:	Zealand Pharma A/S	Protocol Number:	ZP4207-16137
----------	--------------------	------------------	--------------

WHERE wherever; (optional)

RUN;

QUIT;

Note: (Treatment order: 1=drug 1,2= drug 2,3= drug 3, etc... 5= placebo)

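### The ANCOVA for key secondaries 5-8 assumes one residual variance under 2:1:1 allocation, although the rescue rule may give the arms different spreads; direction and size are unknown

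*SAP*

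**What the plan says.** Key secondaries 5-8 are the glucose changes at 30, 20, 15 and 10 minutes. Under SAP Section 4.7.1 they are formal steps in the testing hierarchy. Section 4.7.3.1, repeated in Section 4.10, fits an ANCOVA to each, "with treatment group modelled as a fixed effect and with the baseline plasma glucose modelled as a covariate", and then: "The dasiglucagon versus placebo treatment group difference will be evaluated inferentially as a least squares means contrast". The contrast is tested two-sided at the 5% level.

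Table 4-2 names GLM for these endpoints. The generic ANCOVA template in Section 4.15 is PROC GLM with three-level contrasts such as "ESTIMATE 'T1 - T3' treatment 1 0 -1". That means one residual variance. The wording implies one model for all three arms but does not say so outright.

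On rescue, the rule in Section 4.7.3.1 is: "plasma glucose changes from baseline at rescue carried forward in those subjects who require rescue IV glucose before plasma glucose ≥ 20 mg/dL recovery".

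No unequal-variance model, robust standard error or variance check is planned for these endpoints. Elsewhere the SAP does attend to model assumptions: it checks proportional hazards before using the Cox model (Section 4.7.2.1) and log-transforms the glucose AUC (Section 4.7.4.1).

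**The concern.** A value carried forward from a rescue that precedes recovery lies below +20 mg/dL by construction. Recovered subjects have no such ceiling. If the share of frozen values, or the size of the rise after recovery, differs between arms, so can the variance of the change.

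Unequal variances matter here because allocation is unequal. A pooled variance is weighted towards the larger arm, but the sampling variance of the contrast depends most on the smaller arm. The pooled standard error is then too large if dasiglucagon has the larger spread and too small if placebo has. At stake are the p-values of four formally tested endpoints and any confidence intervals reported with them.

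**Working it through.** **The plan's own figure.** No power or precision is stated for the change endpoints. The only design figure is 90% power for the primary log-rank test (Section 3.9): exponential medians of 10 and 20 minutes, 45 minutes of follow-up, "with 78 subjects treated with dasiglucagon and 39 subjects with placebo".

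- Expected events: 78 × (1 − 2^(−4.5)) + 39 × (1 − 2^(−2.25)) = 74.6 + 30.8 = 105.4.
- Schoenfeld: √(105.4 × 2/3 × 1/3) × ln 2 − 1.96 = 1.39, so power is 91.8%. A simulation of 3,000 trials gives 90.4%.

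The stated figure reproduces. It confirms the arm sizes but says nothing about the ANCOVA.

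**Inputs for the ANCOVA.**

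- Arm sizes: 78 dasiglucagon, 39 placebo, and 156 − 78 − 39 = 39 GlucaGen (Sections 3.1 and 3.9).
- SDs by arm: not in the SAP. Assume dasiglucagon SD = 1, placebo SD = k and GlucaGen SD = 1.

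**Formulas** (covariate ignored).

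- Pooled variance: s² = (77 + 38k² + 38)/153.
- Pooled SE = √[s²(1/78 + 1/39)].
- True SE = √[1/78 + k²/39].

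Example with k = 0.5: s² = 124.5/153 = 0.814. Pooled SE = √(0.814 × 3/78) = 0.177 and true SE = √(1.5/78) = 0.139. The ratio is 1.28.

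| k (placebo SD / dasiglucagon SD) | pooled SE / true SE | simulated coverage of nominal 95% interval |
|---|---|---|
| 0.25 | 1.43 | 99.2% |
| 0.5 | 1.28 | 98.9% |
| 0.67 | 1.17 | 98.0% |
| 0.8 | 1.10 | 96.8% |
| 1.0 | 1.00 | 95.6% |
| 1.25 | 0.91 | 92.6% |
| 1.5 | 0.85 | 90.4% |

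Coverage is from 4,000 simulated three-arm ANCOVAs per row, with a baseline covariate. HC3 standard errors in the same simulations gave 94.7% to 95.9% throughout.

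**How much is due to the third arm.** Pooling dasiglucagon and placebo only, s² = (77 + 38k²)/115. The ratio is 1.23 at k = 0.5 (against 1.28 with GlucaGen) and 0.88 at k = 1.5 (against 0.85). Most of the error is therefore present with two arms. With the GlucaGen SD at 0.8 or 1.2 times the dasiglucagon SD, the three-arm ratio at k = 0.5 is 1.20 or 1.36.

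**Can the direction be settled from the SAP?** With the planning medians, recovery by 30 minutes is 1 − 2^(−3) = 87.5% on dasiglucagon and 1 − 2^(−1.5) = 64.6% on placebo. An arm that mixes recovered subjects (proportion p, mean m, SD s) with unrecovered ones (mean m₀, SD s₀) has variance ps² + (1 − p)s₀² + p(1 − p)(m − m₀)². The factor p(1 − p) is 0.109 on dasiglucagon and 0.229 on placebo, so placebo is the more mixed arm at 30 minutes. It is also the more mixed arm at 20 minutes (0.188 vs 0.25) and 15 minutes (0.229 vs 0.241), but not at 10 minutes (0.25 vs 0.207).

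Illustrations at 30 minutes, with all means and SDs assumed (mg/dL) and unrecovered subjects at mean 5, SD 7:

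- Recovered subjects at mean 60, SD 20 in both arms: arm SDs 26.2 (dasiglucagon) and 31.1 (placebo), k = 1.19, SE 7% too small.
- Recovered subjects at 90 (SD 25) on dasiglucagon and 40 (SD 15) on placebo: arm SDs 36.7 and 21.0, k = 0.57, SE 23% too large.
- Recovery 98% vs 20% (also assumed), recovered subjects at 90 (SD 25) and 30 (SD 10): arm SDs 27.5 and 12.6, k = 0.46, SE 30% too large.

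**The case against.** The strongest reply is that pooled-variance ANCOVA is a standard prespecified analysis, that nothing in this section is contradictory, and that the SAP gives no SD, expected change or rescue rate by arm from which to show harm. This stands, and it limits the point to an improvement.

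Three stronger readings are tempting, and the documents support none of them.

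- **That the interval is likely too wide.** Section 3.9 expects slow placebo recovery, which with larger rises on active drug would point that way. But the rescue rule applies in every arm, and a mixture of frozen and recovered subjects can raise an arm's variance. The planning medians alone allow either direction.
- **That the third arm is the cause.** The two-arm calculation shows otherwise. The Section 4.15 template is also generic (its note codes placebo as level 5), so it is weak evidence of which arms enter the model.
- **That a confirmatory conclusion is at risk.** If the placebo SD is the smaller, with active SDs alike, the test is conservative and only precision and some power are lost. If dasiglucagon did nothing, its distribution would match placebo's and k would be 1. Any distortion would then come only from a different GlucaGen spread, and a larger one makes the test more conservative.

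Section 4.7.3.1 specifies a t-test; an interval for these endpoints comes only through the generic template. What remains is that the planned standard error is correct only if variances are equal (or errors happen to offset), and the rescue rule gives a reason to doubt that they are.

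**Conclusion.** The point holds as a low-cost improvement, not as a demonstrated error. The plan fixes a single residual variance for four endpoints in the hierarchy, under unequal allocation and with a data rule that may make the spreads differ. Over placebo/dasiglucagon SD ratios of 0.5 to 1.5, the standard error of the contrast runs from about 28% too large to 15% too small, and coverage from about 99% to 90%; it is right at a ratio of 1. These figures rest on 78, 39 and 39 subjects, equal SDs in the active arms and normally distributed errors in the simulation. The ratio itself is an assumption, and it may differ among the four time points.

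**What to change.** Before unblinding, amend Sections 4.7.3.1 and 4.10 and Table 4-2. Keep the ANCOVA means model, the carry-forward rule and the testing order. For the dasiglucagon versus placebo contrast, prespecify one of the following:

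- a separate residual variance per arm (PROC MIXED with REPEATED / GROUP=treatment and Satterthwaite degrees of freedom); or
- HC3 standard errors.

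State which arms enter the model, and replace the generic GLM template with the code that will be run.

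The cost is SAP wording, a change of procedure and a few degrees of freedom. If variances prove equal, precision falls slightly: in the simulation at a ratio of 1, the HC3 half-width was 9.81 against 9.71 for the pooled model, about 1% wider. The arm-specific variance model was not itself simulated, but with at least 39 subjects per arm its cost should also be small.

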4.7.4 Secondary clinical efficacy (PD) endpoints

- Time to first plasma glucose concentration of ≥ 70 mg/dL (3.9 mmol/L) without administration of rescue IV glucose.
- Plasma glucose response as area under the curve above baseline from time zero to 30 minutes, $AUC_{0-30min}$.

Secondary clinical efficacy endpoints will be assessed based on plasma concentration data from samples collected at the dosing visit (Visit 2).

Unless otherwise stated, the population base of analysis will be the Full analysis set.

4.7.4.1 Analysis of secondary clinical efficacy (PD) endpoints

1. Time to first plasma glucose concentration ≥ 70 mg/dL from baseline. This time to-event endpoint will be evaluated using a Kaplan-Meier approach, with treatment group as a stratification factor, analogous to that used for the primary endpoint analysis. Differences between the KM curves (dasiglucagon versus placebo, GlucaGen versus placebo) will be evaluated inferentially using pairwise two-sided log rank tests. If the ≥ 70 mg/dL endpoint is not met within 45 minutes post-dosing, the time of the last valid plasma glucose measurement up to 45 minutes will be the censoring time.
2. The AUC will be calculated as the baseline-adjusted area under the plasma glucose profile over time:
 - a. $AUC_{0-30min}$: restricting the time window to the 0 to 30 minutes interval.

The log-transformed AUC endpoint will be analyzed using an analysis of covariance (ANCOVA) model with treatment as fixed effect and baseline plasma glucose modelled as a covariate. The least squares means treatment group differences will be back transformed (anti logged) for presentation as a ratio of the treatment group geometric means, with their corresponding 95% CI.

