The primary endpoint will additionally be analyzed using a Cox proportional hazards (CPH) time to event statistical model, if the hazards by treatment group can be assumed proportional using a graphical comparison of log-minus-log survival curves and no more than two-thirds of the recovery times are censored in each treatment group. The CPH model will be used for descriptive purposes, with treatment group and injection site modeled as categorical effects, and baseline plasma glucose modelled as a continuous covariate. The treatment group rate ratios, active versus placebo, will be estimated together with the 95% confidence intervals, and pairwise treatment group inferences (dasiglucagon vs placebo, GlucaGen vs placebo) will be evaluated using two-sided likelihood ratio tests.

Due to the discrete nature of blood sampling in time, and the fact that there must be a true, but unmeasured, ordering of the recovery times, the method using the “exact discrete” partial likelihood for tied failure times will be applied. In SAS, this is implemented in the phreg procedure with the option ties=discrete. The influence of injection site on time to recovery will also be evaluated in the proportional hazards model by a ‘type 3’ test in the phreg procedure.

To obtain an estimate of these true, but unassessed, patient recovery times, a linear interpolation (between the two time points before and after recovery is observed) will be carried out to estimate the patients’ actual time of recovery. These derived recovery times will be described and analysed in the same manner as for the discrete times above.

CONFIDENTIAL

Sponsor:	Zealand Pharma A/S	Protocol Number:	ZP4207-16137
----------	--------------------	------------------	--------------

Table 4-1: Definition of Events, Censoring, and Populations for Time to Event Analyses

Time to Event Endpoint	Initiating Event	Terminating Event(s)	Censoring Event(s) /Competing Risk(s)	Analysis Sample	Study Endpoint /Statistical Analyses
Time to plasma glucose recovery	Administration of IMP	First increase in plasma glucose of ≥ 20 mg/dL (1.1 mmol/L) from baseline w/out rescue IV glucose admin.	Rescue IV glucose administration will be censored at 45 minutes after IMP dosing	Full analysis set, PP	Primary/ Pairwise two-sided log rank test

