4.12 Subject Withdrawals and Missing Data

Failure is defined for the primary time-to-recovery endpoint as censored with time to recovery set to the maximum follow-up time, here 45 minutes. Individuals will be set to 'failure' in case of receiving rescue IV glucose, discontinuation due to treatment or discontinuation in connection with the induced hypoglycemia state. Only if an intermediate assessment is missing independent of rescue treatment, study treatment or an adverse event including hypoglycemia, a linear interpolation can be applied to impute a missing value.

The same construct of imputation for missing values applies for the analysis of the plasma glucose AUC0-30min.

In the case of subject withdrawal, no imputation of values for PK or PD measurements will be done. Analyses will be done on valid cases only, i.e., no imputation techniques such as last observation carried forward will be applied.

CONFIDENTIAL

Sponsor:	Zealand Pharma A/S	Protocol Number:	ZP4207-16137
----------	--------------------	------------------	--------------

Methods for Handling Missing Dates

All analyses and descriptive summaries will be based on the observed data. For the subject data listings, no imputation of incomplete dates will be applied. The listings will present the incomplete dates without any change.

Missing or Partial Death Dates

- If the entire date is missing, the death date will be imputed as the day after the date of last contact.
- If the day or both day and month is missing, the death date will be imputed to the maximum of the full (non-imputed) day after the date of last contact and the following:
 - If day is missing, day will be 1st of the month
 - If both day and month are missing, death month and day will be January 1st.

Missing Dates in Adverse Events/Concomitant Therapies

Dates missing the day or both the day and month of the year will adhere to the following conventions:

- The missing day of onset of an AE or start date of a therapy will be set to:
 - first day of the month that the event occurred, if the onset yyyy-mm is after the yyyy-mm of first study treatment
 - the day of the first study treatment, if the onset yyyy-mm is the same as yyyy-mm of the first study treatment
 - the date of informed consent, if the onset yyyy-mm is before the yyyy-mm of the first treatment
- The missing day of resolution of an AE or end date of a therapy will be set to:

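### Time to 70 mg/dL: the SAP does not carry over the primary endpoint's failure rule, so related drop-outs are censored early, and rescued subjects may be too

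*SAP*

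**What the plan says.** Section 4.7.4 defines the endpoint as the time to a first glucose of at least 70 mg/dL without rescue IV glucose, so a subject rescued before that point cannot have the event. Section 4.7.4.1 describes a Kaplan-Meier approach "with treatment group as a stratification factor, analogous to that used for the primary endpoint analysis", and then gives its own censoring rule. If the threshold is not met within 45 minutes, "the time of the last valid plasma glucose measurement up to 45 minutes will be the censoring time". That rule mentions neither rescue nor discontinuation, and *valid* is not defined.

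The primary endpoint is handled differently. Table 4-1 states: "Rescue IV glucose administration will be censored at 45 minutes after IMP dosing". Section 4.12 states: "Failure is defined for the primary time-to-recovery endpoint as censored with time to recovery set to the maximum follow-up time, here 45 minutes". It applies this "in case of receiving rescue IV glucose, discontinuation due to treatment or discontinuation in connection with the induced hypoglycemia state". The rule is limited to the primary endpoint. The next paragraph extends the missing-value construct to the glucose AUC over 0 to 30 minutes, but not to time to 70 mg/dL. Section 4.12 also says: "In the case of subject withdrawal, no imputation of values for PK or PD measurements will be done".

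For the primary, censoring at the time of rescue is only a sensitivity analysis (sections 4.7 and 4.7.2.1). The primary log-rank test is stratified by injection site (4.7.2.1), as is the test for time to first rescue (4.9.4), and randomization is stratified by it (3.7). The tests in 4.7.4.1 are not described as stratified by site.

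**The concern.** Kaplan-Meier treats a censored subject as having the same future chance of the event as those still at risk. A subject whose sampling stops because of hypoglycemia or of the treatment, or who needs IV glucose, is among the least likely to reach 70 mg/dL unaided. Removing such subjects early lets the remaining subjects stand in for them, which raises the estimated recovery curve. If this is more common on placebo, the placebo curve rises most and the difference from dasiglucagon shrinks.

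The failure rule prevents this for the primary. For time to 70 mg/dL the text points two ways: the method is called analogous to the primary, but the explicit censoring rule differs. A programmer would normally follow the explicit rule, and would then have to decide alone what *valid* means after rescue.

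**Working it through.** **The plan's own figure.** The SAP gives no rescue rate, median or power for this endpoint. Its only related figure is 90% power for the primary (section 3.9: 78 versus 39 subjects, exponential medians 10 and 20 minutes, 45 minutes of follow-up).
- Expected events: 78 × (1 − 2^−4.5) + 39 × (1 − 2^−2.25) = 74.6 + 30.8 = 105.4.
- Schoenfeld: √(105.4 × 2/3 × 1/3) × ln 2 − 1.96 = 3.35 − 1.96 = 1.39, which gives 91.8%. The exponential-variance form gives 89.9%. The figure reproduces.

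**Step 1: who is censored when.**

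| Subject not reaching 70 mg/dL | Primary rule applied | Section 4.7.4.1 as written |
|---|---|---|
| Complete sampling, no rescue | 45 min | 40 min |
| Sampling stops because of treatment or hypoglycemia | failure at 45 min | last sample before stopping |
| Rescued, later samples valid | failure at 45 min | 40 min |
| Rescued, later samples not valid | failure at 45 min | last sample up to rescue |

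The 40 minutes follows from section 3.3.2, which schedules samples at 40 and 50 minutes and none between.

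**Step 2: 40 versus 45 minutes.** A subject censored at 40 is still in the risk set at 40, and on the nominal grid no event can be observed between 40 and 45. The two rules therefore give the same curve and test. In simulated trials of 78 versus 39 the log-rank z was identical every time (maximum difference 0.0). Rows 1 and 3 do no harm.

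**Step 3: size for rows 2 and 4.** Assumptions, none from the SAP: a fraction p of placebo subjects is rescued or stops at 10, 12, 15, 17, 20, 25 or 30 minutes with equal chance and would not reach 70 mg/dL unaided. The rest are exponential with a 30-minute median, observed on the sampling grid.

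Failure rule: recovery by 40 min = (1 − p) × (1 − 2^(−40/30)) = (1 − p) × 0.603.

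Early censoring: 1 − Π(1 − d/n), where at each sample d = (1 − p)(2^(−s/30) − 2^(−t/30)) and n = (1 − p) 2^(−s/30) + p × (share of the p group not yet censored), with s the preceding sample time. For p = 0.4:
- At 12 min, n = 0.476 + 0.343 = 0.819 and d = 0.0215.
- At 40 min the p group has gone, so n = 0.300 and d = 0.0619.
- Recovery to 30 min is 0.371, so recovery to 40 min is 1 − 0.629 × (1 − 0.0619/0.300) = 0.501.

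| p | Failure at 45 | Censored at rescue or stop | Gap (points) |
|---|---|---|---|
| 5% | 57.3% | 59.2% | 1.9 |
| 10% | 54.3% | 58.1% | 3.8 |
| 20% | 48.3% | 55.6% | 7 |
| 40% | 36.2% | 50.1% | 14 |
| 60% | 24.1% | 43.3% | 19 |

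Censoring one sample earlier, at the last one before rescue, gives 57%, 52% and 47% in the last three rows, gaps of about 8, 16 and 23 points.

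**Step 4: effect on the test.** A second set-up borrows the primary's medians (10 and 20 minutes), draws rescue times from an exponential distribution independent of recovery, and sets the dasiglucagon rescue hazard to one tenth of placebo. With 11%, 21%, 36% and 55% of placebo subjects rescued first, placebo recovery without rescue is 69%, 63%, 54% and 41% under the failure rule, against about 75% throughout under pre-rescue censoring. Mean log-rank z is 3.5, 3.8, 4.3 and 5.0 against 3.0, 3.0, 2.9 and 2.6. Because rescue is independent of recovery here, the 75% is what would be seen if nobody were rescued, which is not the endpoint in section 4.7.4.

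**The case against.** The strongest defence is that the SAP nowhere says rescued subjects are censored at or before rescue. Sampling runs to 90 minutes with no stop at rescue. The first primary sensitivity analysis, which does not censor rescued subjects, needs their later samples to be usable. Where the SAP wants censoring at rescue it says so, and section 4.7.4.1 does not. *Valid* is used for drug concentrations in section 4.7.5.1 with no link to rescue. On this reading rescued subjects are censored at 40 minutes and step 2 shows no effect. This stands. A reader might infer that the plan certainly overstates placebo recovery by censoring rescued subjects early; the document does not support that.

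The endpoint is also listed among the other secondary endpoints, outside the hierarchy of section 4.7.1, and any bias arising mainly on placebo works against dasiglucagon, so false-positive risk is not raised. This stands too. Nor would a different result contradict the primary: reaching 70 mg/dL and rising by 20 mg/dL are different events.

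The defence does not cover subjects whose sampling stops because of treatment or hypoglycemia. They have no later samples, the failure rule is confined to the primary, and section 4.12 rules out imputation after withdrawal.

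On stratification, an unstratified test is legitimate for a non-confirmatory endpoint, and section 4.7.2.1 allows later presentations to drop injection site if it shows no effect. That makes the omission minor, but the SAP gives no reason for it.

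**Conclusion.** The point holds in a limited form. As written, section 4.7.4.1 censors treatment- or hypoglycemia-related drop-outs informatively at their last sample. No rate is given for them; at an assumed 5% or 10% of placebo subjects the overstatement would be about 2 or 4 points. For rescued subjects the effect depends on one undefined word. It is zero if post-rescue samples count as valid. If they do not, it is about 7 to 19 points at 40 minutes, under the assumed 20% to 60% rescued, rescue at 10 to 30 minutes, no unaided recovery in those subjects and a 30-minute median in the rest (up to about 23 points if censored one sample earlier). The SAP supplies none of these inputs. Where the effect exists and rescue is commoner on placebo, it shrinks the drug effect on a non-confirmatory endpoint that still gets inferential log-rank tests and has no planned rescue sensitivity analysis. The missing injection-site stratification is a minor inconsistency with randomization and the primary test.

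**What to change.** Before unblinding, replace the censoring rule in section 4.7.4.1 with the following:

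- A subject who receives rescue IV glucose, or who discontinues because of treatment or the induced hypoglycemia, before reaching 70 mg/dL is set to not recovered and censored at 45 minutes, as section 4.12 does for the primary.
- Censoring at the last sample is kept only for missing data unrelated to these reasons.
- Censoring at the time of rescue is reported as a sensitivity analysis, as for the primary.
- The log-rank tests are stratified by injection site.

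Extend section 4.12 to name this endpoint. The cost is a few sentences. The derivation and the stratified test already exist for the primary, and no new data are needed.
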